4.5. Secondary Analyses

To support the secondary study objectives, analyses will include:

- determination of the proportions of patients with COVID-19-related hospitalizations up to Days 29, 60, and 90
- COVID-19-related ER visits up to Days 29, 60, and 90
- Description of AEs and SAEs up to 2 hours, 24 hours, Days 29, 60, and 90.

Descriptive analyses for these secondary objectives will follow the same statistical methodology as used for the primary analysis.

COVID-19-related ED visits, AEs, and SAEs defined in Section 3.5 will be summarized by numbers and percentage up to 2 hours, 24 hours, and 29, 60, and 90 days after infusion. A listing of AE data for patients at any time during the study will be provided, including age, gender, race, the description of AE, start date, stop date, time from infusion (in days), and severity.

Exposure to Therapy

Exposure to therapy will be listed, including timing of infusion, planned dose, total dose administered, treatment interrupted, and reason for interruption. Exposure to therapy will be represented as the total number of complete and incomplete infusions and will be summarized using descriptive statistics.

Adverse Events

Although all AEs after signing the ICF are recorded by the site in the CRF/EDC, SAE reporting to the sponsor begins after the participant has signed the ICF and has received study intervention. However, if a SAE occurs after signing the ICF, but prior to receiving study intervention, it will be reported within the SAE reporting timeframe if it is considered reasonably possibly related to study procedures.

Adverse events will be coded according to the Medical Dictionary for Regulatory Activities (MedDRA). Summaries of AEs will include the number of participants with at least 1 AE. When reporting by System Organ Class (SOC) and Preferred Term (PT), the reports will present the SOC in alphabetical order; PTs within the SOCs will be presented in order of decreasing frequency of occurrence overall. A patient with multiple AEs (different PTs) coded to the same SOC will be counted only once for that SOC but will be counted each time for different PTs within that SOC. A patient with separate events of the same PT will be counted only once in the frequency tables for that PT.

The number and percentage of participants who experienced an AE, SAE, AE related to study drug, died due to an AE, discontinued from the study treatment, or discontinued from the study due to an AE will be summarized by during infusion and after infusion for up to 2 hours, 24 hours, 29 days, 60 days, and 90 days. The summary method for each event type is described in [Table 4.1](#).

Table 4.1 Types of Adverse Events to be Summarized

Event Type	Summary Method
SAE	SAEs will be summarized for study participants by SOC and PT. These reports will also include the total number of SAE for each SOC and PT.
AE Resulting in Death	If there are any AEs that result in death, a listing of all deaths will be provided. In addition, a summary table may also be created by PT in order of decreasing frequency of PT.
AE Leading to Study Drug Discontinuation	AEs for which the action taken with medication as 'Drug Withdrawal' will be identified as AEs that lead to study drug discontinuation. The AEs that lead to study drug discontinuation will be summarized by SOC and PT for the safety population. A by-patient listing of the AEs that lead to study drug discontinuation will also be provided.
Treatment-Related AE	Every AE will be assessed by the investigator for its relationship to the study treatment.
AE by Maximal Severity	Every AE will be graded by the investigator as mild, moderate, or severe, so for each patient the greatest severity observed can be obtained by comparing the severity of all of a patient's AEs that share the same SOC or PT. A table of AEs by maximal severity will be prepared by SOC and PT.
AE (Not Including Serious)	The most common, nonserious AEs will be summarized. All PTs that occur in at least 1% of the safety population participants, when not counting the serious AEs, will be tabulated by SOC and PT. These reports will also present the total number of AEs for each SOC and PT.

Abbreviations: AE = adverse event; PT = Preferred Term; SAE = serious adverse event;
SOC = System Organ Class.

Infusion Site Reactions

Infusion site reactions are AEs localized to the immediate site of the administration of a drug and will be defined using terms from the MedDRA High-Level Term, Infusion Site Reactions. All ISRs will be listed.

The number and percentage of patients with AEs related to infusion sites, SAEs related to infusion sites, and AEs related to infusion sites resulting in study drug discontinuation will be summarized using MedDRA PT. Events will be ordered by decreasing frequency.

The number and percentage of patients with AEs related to infusion sites by maximum severity will be summarized using MedDRA PT.

Hypersensitivity, Anaphylactic, and Infusion-Related Reactions

Hypersensitivity reactions is used as an overarching term to describe events that are systemic or localized reactions that likely have an allergic/hypersensitivity etiology. At all visits in Phase 3 clinical studies, patients will be evaluated by the investigator for signs and symptoms suggestive of hypersensitivity. Investigators will complete a CRF designed to record additional information about AEs suggestive of a hypersensitivity reaction.

Two main analyses are performed respectively assessing (a) potential immediate hypersensitivity, including anaphylaxis and IRRs, and (b) potential nonimmediate hypersensitivity.

Time Period A, of potential immediate hypersensitivity, includes all AEs occurring on the day of study drug administration.

Time Period B, of potential nonimmediate hypersensitivity, includes all AEs occurring strictly after the day of study drug administration.

Analyses for both time periods are based on the following Standard MedDRA Queries (SMQs):

- Anaphylactic reaction SMQ (20000021; narrow and broad)
- Hypersensitivity SMQ (20000214; narrow and broad), and
- Angioedema SMQ (20000024; narrow and broad).

Additionally, for the Anaphylactic reaction SMQ in Time Period A, the algorithmic query (per the MedDRA Maintenance and Support Services Organization [MSSO] SMQ guide) will be performed. An algorithmic case must include either

- a narrow term from the SMQ (Category A of the SMQ), or
- multiple terms from the SMQ comprising terms from at least 2 of the following categories from the SMQ
 - Category B - (Upper Airway/Respiratory)
 - Category C - (Angioedema/Urticaria/Pruritus/Flush), or
 - Category D - (Cardiovascular/Hypotension).

Where algorithm is mentioned below, this applies only to Time Period A.

The number and percentage of patients reported with an AE for the following will be analyzed for each of the 2 time periods:

- any narrow or algorithmic term from any 1 of the 3 SMQs indicated above (that is, combined search across narrow and algorithmic portions of all 3 SMQs)
- any narrow term within each SMQ, separately (that is, narrow SMQ search), and
- any term within each SMQ, separately (that is, broad SMQ search).

Within queries, individual PTs that satisfied the queries will be summarized.

For Time Period A only, the number and percentage of each PT that is not in any of the 3 SMQs (that is, other events occurring on the day of study drug administration) will be summarized overall and by individual PT. Only PTs that occur in at least 3 patients receiving bamlanivimab will be displayed in this portion of the table.

The PTs will be arranged in the summary in decreasing order of frequency for patients in the total bamlanivimab treatment group. Note that an individual patient may contribute multiple events. Also, a single event may satisfy multiple SMQs, in which case the event contributes to every applicable SMQ.

The analyses above are the starting point for medical interpretation of any apparent differences between treatment groups. For notable events, case review will be applied to make the final determination of whether an event is most accurately described as a potential hypersensitivity reaction to a drug or another event that is not clearly associated with drug administration. This judgment will be on the basis of totality of information available, including the content of the follow-up CRF collected for potential hypersensitivity events.

Vital Signs and Other Physical Findings

The measurements analyzed for vital signs and physical characteristics include systolic blood pressure (BP), diastolic BP, pulse, peripheral oxygen saturation, respiratory rate, and temperature, if data warrant.

Given different total volumes of solution for administration of 700mg bamlanivimab (200ml, 100ml, and other volume which will be entered in the CRF by site), the infusion duration will differ, such as about 1 hour for the total amount of 200 ml, and about 30 minutes for the total amount of 100 ml. For this reason, vital signs will be summarized at the following timepoints: baseline, half infusion, end of infusion, 30 minutes post-infusion, and 1 hour post-infusion, rather than using the recommended timing (immediately before the infusion, every 15 minutes during the infusion, and every 30 minutes for at least 1 hour after the infusion). Baseline is defined as the last non-missing value before patient's bamlanivimab infusion.

Vital signs data will be summarized by box plots for observed values, along with changes from baseline by timepoints.

Box plots for observed values by timepoints will include participants with a non-missing value at the timepoint. Values outside 1.5 interquartile range (IQR) below 25% and above 75% will be shown as outliers. Descriptive summary statistics will be included in a table below the box plot.

Box plots for change from baseline values to each post baseline timepoints will be presented similarly to those for observed values by timepoints described above. They will include participants with a non-missing value at the timepoint, and values outside 1.5 IQR below 25% and above 75% will be shown as outliers. Descriptive summary statistics will be included in a table below the box plot.

All vital signs and other physical findings for individual participants will be listed.

Protocol Violations

Protocol violations will be identified throughout the study. Important protocol deviations (IPDs) are defined as those deviations from the protocol that would potentially compromise participants' safety, data integrity, or study outcome.

The number and percentage of participants having IPDs will be summarized within each category and subcategory of deviations. A by-patient listing of IPDs will be provided.

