Vital signs		X						
Includes: body temperature, pulse rate, BP, respiratory rate, SpO2, and supplemental oxygen flow rate, FiO2 if known, and method of delivery, if applicable.
 
Record SpO2 while participant is at rest.
 
Day 1 recommended timing of vitals:
 
 
immediately before the infusion
 
every 15 minutes during the infusion, as possible, and
 
every 30 minutes for at least 1 hour after the infusion.
 
 
During infusion, record pulse rate, BP and SpO2. Automation may be used. See Section 8.2.2 for data collected on CRF.

Study J2X-MC-PYAJ	Screen	Infusion Day						
Study Day		1	2	29	60	90	ED	Screening and Day 1 procedures may occur on the same day. Day 2 = telephone call 24 hours post-infusion Day 29, 60, 90 = EMR and/or telephone call review as necessary
Visit Window (± number of days)		--	2*	5	7	7		Visits may not be combined. *Day 2 call visit window +2 only
Hospitalization events		X*	X	X	X	X	X	*Post-infusion only (otherwise exclusion criterion) Record if the following events occur or occurred since prior visit: 

• Emergency room visits

• hospitalized

• ICU admittance,

• Extended care facility admittance, and

• Discharge

Death		X	X	X	X	X	X	From COVID-19-related causes

Abbreviations: AE = adverse event; BP = blood pressure; CRF = case report form; ED = early discontinuation; FiO2 = fraction of inspired oxygen in the air; ICU = intensive care unit; NSAIDS = non-steroidal anti-inflammatory drugs; SpO2 = saturation of peripheral oxygen.

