## **6.4. Study Intervention Compliance**

Participants will receive study intervention directly from the investigator or designee, under medical supervision. The date and time of dosing will be recorded in the source documents and recorded in the CRF. The dose of study intervention and study participant identification will be confirmed at the time of dosing by a member of the study site staff other than the person administering the study intervention.

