#### 8.2.1. Vital Signs

Vital signs will be measured as specified in the SoA (Section 1.3) at the infusion visit. Vital signs include

- body temperature
- blood pressure
- pulse rate
- respiration rate
- saturation of peripheral oxygen, and
- supplemental oxygen flow rate, FiO2 if known, and method of delivery, if applicable.

Additional vital signs may be measured during the study if warranted, as determined by the investigator.

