3.2. Data Collection

Data for bamlanivimab-treated patients will be captured at the infusion visit (Day 1), at 24 hours post-infusion (Day 2), and at subsequent follow-up periods (Days 29, 60, and 90). Case report form (CRF) data documented within the EDC system will be captured on-site on Day 1 and via telephone call on Days 2, 29, 60, and 90. The EMR records will be extracted during 1 year prior to and 90 days post the infusion date.

Sample Size Determination

Due to early termination, the study enrolled 109, rather than the anticipated 500-3000, bamlanivimab-treated patients. Given that the revised primary objective is to determine the proportion of patients with COVID-19-related hospitalization or all-cause death up to 29 days among bamlanivimab-treated participants and without the use of a comparison group, the observed sample size was 109 participants. This achieved sample size of 109 participants will allow for estimating the proportion with a precision of $\pm 4.4\%$ ($=1.96*\sqrt{(p(1-p)/n)}$) under the assumption of normal approximation of a binomial distribution at a 2-sided significance level of 0.05 and 6% of the true rates of COVID-19-related hospitalization or all-cause death.

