3.7. Variables/Measures

The following variables will be defined based on the EDC/EMR data.

Table 3.1 Variable Definitions/Data Source

Variables	Definition	Data Source
Demographics		
Age at index date, year	Age: whole numbers calculated from bamlanivimab index date Age group: Age ≥ 65 ; Age 55 to 64; Age 18 to 54; and Age 12 to 17	From EMR
Sex	Female and male	From EMR
Race	American Indian / Alaskan Native Asian Black / African American Native Hawaiian / Pacific Islander White Multiple	
Ethnicity	Hispanic, non-Hispanic	
Weight, kg	Continuous variable	
Height, cm	Continuous variable	
BMI	Calculated as $BMI = \text{kg}/\text{m}^2$ where kg is a person's weight in kilograms and m^2 is their height in meters squared. Continuous and categorical ≤ 25 ; 25 to < 30 ; and ≥ 30	From EMR
Tobacco use	current use, former, and never	
Vital signs	
 • body temperature • pulse rate • systolic blood pressure • diastolic blood pressure • respiratory rate • SpO₂ 	From EMR

Variables	Definition	Data Source
	
 supplemental oxygen flow rate FiO2 and method of delivery, if applicable 	
COVID-19 symptoms	
Total of 8-binary indicator variables will be created for the below symptoms:
 
 fever cough sore throat malaise chills loss of sense of taste loss of sense of smell fatigue. headache muscle pain gastrointestinal symptoms shortness of breath with exertion 
The date of COVID-19 symptom onset is defined as the earliest start date of symptoms suggestive of SARS-CoV-2 infection; calculated by difference of bamlanivimab index date and reported symptom date
	From EMR
Days since COVID-19 symptom onset.	Calculated as the difference index date and COVID-19 symptom onset date. Category: ≤8 days and >8 days	
Type of COVID-19 diagnosis test	RT-PCR, antigen testing COVID-19 diagnosis date	

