Preexisting conditions and medical history during 1 year prior to the infusion	
Binary indicator variables will be created for the below:
 
 chronic kidney disease diabetes (type I, type II) immunosuppressive disease currently receiving immunosuppressive treatment cardiovascular disease hypertension chronic obstructive pulmonary disease or other chronic respiratory disease sickle cell disease congenital or acquired heart disease neurodevelopmental disorders medical-related technological dependence; for example, tracheostomy, gastrostomy, or positive pressure ventilation (not related to COVID-19) asthma, reactive airway or other chronic respiratory disease that requires daily medication for controls 	From EMR

Variables	Definition	Data Source
Treatments of special interest prescribed within 30 days prior to infusion (exclusive infusion date)	Dates of: 
 • NSAIDs • antivirals • antibiotics • anti-malarials • corticosteroids • immunomodulators • other investigational treatments (including ivermectin, COVID-19 vaccine, and oxygen) 	From EMR
Prior or concomitant therapy 90 days before and 90 days after infusion	Dates of: 
 • NSAIDs • antivirals • antibiotics • anti-malarials • corticosteroids • immunomodulators 	From EMR
Procedures of special interest during 10 days prior infusion	Dates of: 
 • supplemental oxygen • non-invasive ventilation • high flow oxygen device • mechanical ventilation • Extracorporeal membrane oxygenation (ECMO) • additional organ support 	From EMR
Respiratory support	Dates of: 
 • high flow nasal cannula • noninvasive positive pressure ventilation 	From EMR
Mortality	
 • date • cause of death 	From EMR
Pregnancy	Date of confirmed pregnancy	From EMR

Abbreviations: BMI = body mass index; COVID-19 = coronavirus disease 2019; EMR = electronic medical record; FiO₂ = fraction of inspired oxygen in the air; NSAID = nonsteroidal anti-inflammatory drug; RT-PCR = reverse transcription-polymerase chain reaction; SARS-CoV-2 = severe acute respiratory syndrome coronavirus 2; SpO₂ = saturation of peripheral oxygen.

4. Statistical Analyses

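### The vital-sign baseline rule has no time limit, so where a Day 1 pre-infusion reading is missing, an older EMR value can serve as baseline

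*SAP*

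**What the plan says.** In the vital-signs part of SAP 4.5, the baseline definition begins "Baseline is defined as the last non-missing value before" and ends at the patient's infusion. No day, visit or look-back window is attached. The same part lists five summary timepoints: baseline, half infusion, end of infusion, and 30 minutes and 1 hour afterwards. It then plots observed values and changes from baseline. A participant enters a change plot if a value is present at that timepoint.

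On the source, the text above Table 3.1 in SAP 3.7 says "The following variables will be defined based on the EDC/EMR data". The vital-signs row itself names the EMR and gives no time frame. SAP 3.2 states "The EMR records will be extracted during 1 year prior to and 90 days post the infusion date". It also says "Case report form (CRF) data documented within the EDC system will be captured on-site on Day 1".

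On measurement, Protocol 8.2.1 states "Vital signs will be measured as specified in the SoA (Section 1.3) at the infusion visit". The Schedule of Activities (Protocol 1.3) marks vital signs on Day 1 only and lists a reading "immediately before the infusion", under a heading that calls the Day 1 timing recommended. Protocol 6.4 adds "The date and time of dosing will be recorded in the source documents and recorded in the CRF".

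**The concern.** Change from baseline during and shortly after an infusion is informative only if the baseline reflects the patient's state on arrival. These participants are symptomatic by inclusion criterion 3, with symptoms that can include fever and shortness of breath on exertion. A reading from a routine visit months earlier would describe a different clinical state.

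If such a reading serves as baseline, a raised temperature or pulse, or a lower SpO2, that the patient already had on arrival would be plotted as change during or after infusion. A real change in the opposite direction could be masked. SAP Version 3 has no control group, so no comparison arm would show that the shift came from the baseline and not from the infusion.

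**Working it through.** The plan states no figure for this point, so there is none to reproduce. The check sets the passages side by side and then sizes the effect under stated assumptions.

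**1. Which value does the rule select?** There are three cases for a given patient and sign.
- A Day 1 pre-infusion reading is available: it is the most recent one, so the rule selects it. No error.
- No Day 1 pre-infusion reading, but an earlier one lies in the extract: the rule selects the earlier one, whatever its date.
- No earlier reading at all: baseline is missing and no change can be computed.

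Only the second case is a problem.

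**2. Does the text exclude the second case?**
- The baseline definition has no window, and neither does the vital-signs row of Table 3.1.
- Other rows of that table do have windows. One is headed "Preexisting conditions and medical history during 1 year prior to the infusion"; others use 30 days, 90 days or 10 days around infusion.
- Exclusion criterion 10 sets limits for SpO2, respiratory rate and heart rate, so a current-illness assessment of those signs is expected. It sets none for temperature or blood pressure.
- The Schedule of Activities has no vital-signs entry at Screening. A value dated before Day 1 therefore comes from outside the scheduled vital-sign assessments.
- The Schedule of Activities refers to Protocol 8.2.2 for what the CRF collects, but that section lists hospitalization events. The documents do not establish that CRF readings would fill a gap in the EMR.

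The second case is therefore possible under the text, and its frequency is not given.

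**3. Size.** Let d be the true pre-infusion value minus the old value, averaged over affected patients. Let f be the share of patients at a timepoint whose baseline is old.
- Observed change for an affected patient = true change + that patient's difference.
- Mean observed change = mean true change + f × d.

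Because a patient's baseline is fixed, the same false amount recurs at every later timepoint where that patient has a value.

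SAP 4.7 gives 109 treated participants. Both f and d are assumptions; d is set at 10 units of whichever sign is plotted, and all 109 are taken as plotted.

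| Assumed f | Patients (f × 109) | Shift in mean change (f × 10) |
|---|---|---|
| 0% | 0 | 0 |
| 1% | 1.09, about 1 | 0.1 |
| 5% | 5.45, about 5 | 0.5 |
| 10% | 10.9, about 11 | 1.0 |
| 25% | 27.25, about 27 | 2.5 |

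At small f the mean hardly moves, but an affected patient can still appear as a false outlier under the 1.5 IQR display rule.

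**The case against.** The strongest reply is that the documents already place the baseline reading at the infusion visit. Protocol 8.2.1 says the signs will be measured there, and the word recommended governs the timing of readings, not whether they are taken. In SAP 4.5 the five timepoints replace the protocol's schedule, and baseline occupies the place of the immediate pre-infusion reading. This stands for every patient and sign with that reading on file. It does not settle what happens when the reading is absent, and that is where the literal rule reaches further back.

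A second reply is that EMR-only sourcing is not certain, since Table 3.1 is introduced as drawing on both EDC and EMR and CRF data are captured on Day 1. That also stands. It is a reason to name the source, not evidence that the gap is closed.

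A third reply is that acute infusion effects are covered elsewhere: adverse events during infusion and up to 2 and 24 hours, infusion site reactions, and the hypersensitivity analyses with case review. Observed values are plotted separately and all individual values are listed. This limits the consequence. The listings let a careful reader find an odd baseline, but they do not correct the change plots or the summary tables beneath them.

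A reader might infer that the SAP adopts a one-year look-back for baseline. It does not: the year is the extraction period for EMR data in general, and the open window follows only from the absence of a limit. A reader might also infer that an affected patient distorts every change plot. The SAP includes a patient only at timepoints where that patient has a value, and the Schedule of Activities lists only pulse, blood pressure and SpO2 for recording during infusion. A false temperature change would therefore arise mainly after the infusion.

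**Conclusion.** The concern holds in a limited form. As written, the rule permits a reading from before Day 1, possibly from before the illness, to serve as baseline whenever the Day 1 pre-infusion reading of a sign is missing. Illness-related change would then be shown as change during or after infusion.

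The number of affected patients is unknown and may be zero. The shift in the mean is f × d, and the documents supply neither quantity, so the table above shows scale and is not an estimate. The effect is confined to a descriptive, single-arm safety display that the SAP makes conditional on the data warranting it. No primary result changes, nor do the secondary hospitalization, ER-visit or adverse-event proportions.

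It may be tempting to extend the point to weight, height and BMI, which also lack a time frame in Table 3.1. The documents do not support that: the SAP plans no change-from-baseline analysis for them. The correction is still worth making, because it is cheap and keeps illness effects out of a display meant to describe the infusion period.

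**What to change.** In SAP 4.5, define the vital-sign baseline as the last value recorded on Day 1 before the recorded start of infusion. If there is none for a sign, treat that baseline as missing: keep the patient in the observed-value plots and leave the patient out of the change-from-baseline plots for that sign. State whether EDC or EMR supplies the value, and which takes precedence if both do. Reporting the number of patients without a Day 1 baseline for each sign would show readers whether the issue arose.

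The cost is one or two sentences and a date-and-time filter; the dosing time is already collected. The downside is slightly fewer patients in the change plots, including any whose only current-illness reading came from a screening contact before Day 1. If Day 1 readings are complete, the output is unchanged.
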